#### 528   **Withdrawal Criteria**

530       - The subject may withdraw at will at any time during the trial.  
531       - Pregnancy or intention of becoming pregnant.  
532       - The subject may be withdrawn at the discretion of the investigator due to non-  
533           compliance or due to a safety concern  
534       - The subject will be withdrawn if starting any drugs that interfere with glucose metabolism  
535           (steroids doses equivalent to prednisone > 5 mg/day)  
536       - The subject may be withdrawn if diagnosed with acute pancreatitis (defined as meeting 2  
537           of the following 3 rules: typical abdominal pain, amylase/lipase > 3x UNL and/or  
538           characteristic US, CT or MRI findings)  
539       - If the fasting or mean SMBG during 3 consecutive days is > 300 mg/dl, the investigator  
540           will schedule an unplanned visit as soon as possible, to obtain confirmatory fasting BG  
541           and investigate the cause. If no apparent or intercurrent cause is detected, the patient  
542           may be withdrawn.  
543       - Unable to comply with trial protocol, at investigator discretion.

#### 544   **Subject Replacement**

546   There will be no replacement of subjects withdrawn after randomization in this trial.  
547  
548

549  
550  
551 **Rationale for Study Population**

552 The target population will include subjects with uncontrolled T2D with HbA1c  $\geq 9\%-15\%$ ,  
553 treated with oral anti-diabetic agents and low dose basal insulin (TDD  $\leq 50$  units/d), in whose  
554 treatment intensification is recommended. Subjects should have been on oral anti-diabetic  
555 agents or basal insulin for at least 90 days (with stable doses of insulin, 10% of dose  
556 fluctuations are acceptable). These subjects need intensification of therapy, and should start  
557 basal insulin and progressively step-up to basal-bolus insulin per national guidelines. However,  
558 these patients may benefit more from a simpler regimen consisting of a single daily injection,  
559 with lower risk of hypoglycaemia and less weight gain, which could improve treatment  
560 adherence. IDegLira is an attractive therapeutic option for these patients for its potency,  
561 flexibility, and potential lower risk of hypoglycaemia and weight gain.

562  
563 **Visit Procedures**

564 Figure 2 and Table 1 provides a description of procedures to be performed at each visit  
565 during the study period. Visits will be distributed as follows: initial/screening visit/CGM baseline  
566 insertion, (visit 1), 2 weeks of screening/run-in period, randomization visit (visit 2), 26-week  
567 treatment period (visits 4-18), and a follow-up safety visit after the end the 26- weeks treatment  
568 period (visit 19). Subjects will have contact with the study team via clinic visits or phone  
569 contacts for a total of 9 clinic visits and 9 telephone contacts. If subjects cannot participate in a  
570 scheduled visit (+/- 3 days), the investigators will arrange for an urgent (as soon as possible)  
571 visit. During follow-up, we will collect the following data (as described in Table 1): glycemic  
572 data, hypoglycemia events, drug compliance, protocol adherence, body measurements, and  
573 adverse events.

574  
575 **Definitions:**

576 • CGM Hypoglycemia: CGM glucose levels  $< 70$ ,  $< 54$ ,  $\leq 40$  mg/dl, with a duration at least  
577 15 minutes by CGM. The end of the event will be when glucose is  $\geq 70$  mg/dl for 15  
578 minutes. A prolonged hypoglycemic event will be defined as CGM levels  $< 54$  mg/dl for  
579 120 minutes or more".

580 • We will only analyze CGM data collected after the first 24 hours from insertion. Patients  
581 should have worn the CGM for at least  $> 4$  days.

582 • Documented symptomatic hypoglycemia, defined as an event with typical symptoms of

hypoglycemia confirmed by SMBG or CGM (< 70 mg/dL and < 54 mg/dL) that occurs at any time of the day

- Incidence of asymptomatic hypoglycemia, defined as no typical symptoms reported by the subject but detected by SMBG or CGM (<70 mg/dL and < 54 mg/dL)
- Incidence of severe hypoglycemia, defined as severe cognitive impairment requiring assistance from another person
- Incidence of nocturnal symptomatic hypoglycemia, defined as an event with typical symptoms of hypoglycemia confirmed by SMBG or CGM < 70 mg/dL and < 54 mg/dL that occurs between 00:00 and 05:59 hrs
- Incidence of nocturnal asymptomatic hypoglycemia, defined as no typical symptoms reported by the subject but detected by SMBG or CGM (<70 mg/dL and < 54 mg/dL) between 00:00 and 05:59 hrs
- Confirmed hypoglycaemia includes: severe hypoglycemia and episodes with or without symptoms with biochemical confirmation of glucose < 54 mg/dL.
- Relative hypoglycemia includes: typical symptoms but with glucose > 70 mg/dL

## Body measurements (Visits V1, V2, V6, V10, V12, V13, V15, V17)

**Body weight:** Body weight should be measured in kilogram or pound, without shoes and only wearing light clothing.

**Height:** Height (without shoes) should be measured in centimeters or inches and recorded without decimals.

**Waist and hip circumference:** The waist circumference is defined as the minimal abdominal circumference located midway between the lower rib margin and the iliac crest. The hip circumference is defined as the widest circumference around the buttocks. Three consecutive measurements of waist and hip circumference should be taken and recorded. Mean values will be used for result analysis. The waist and hip circumferences will be measured to the nearest 1.5 cm (0.2 inches) using a non-stretchable measuring tape.

The subject should be measured in a standing position with an empty bladder and wearing light clothing with accessible waist and hip. The tape should touch skin, but not compress soft tissue and twist in tape should be avoided. The subject should be asked to breathe normally and the measurement should be taken when the subject is breathing out gently.

**Body Mass Index (BMI):** BMI will be calculated by the formula  $\frac{\text{Body weight (Kg)}}{\text{m}^2}$ . Screening Visit: (visit 1, week -2)

Approximately 2 weeks prior to starting study medications, all potential study subjects will be

619 screened to check their eligibility. After providing the subjects with detailed information about the  
620 trial, subjects will sign the informed consent form and will be assigned a patient identification  
621 number.

622 During this visit, investigators will perform a comprehensive assessment, including:  
623 present and past medical history (concomitant illness), diabetes history (onset, prior  
624 complications, current and prior anti-diabetes medication's duration, allergies, or intolerances),  
625 physical examination, height, weight, vital signs, laboratory assessment (HbA1c, chemistry,  
626 pregnancy test for women of child-bearing potential (WOCBP), documentation of current  
627 medications, and prior intolerances or allergies. Investigators will notify the primary care  
628 physician that the subjects have consented to participate in the study. In WOCBP, the  
629 contraceptive methods will be documented.

630  
631 After review of all inclusion and exclusion criteria, including laboratory results, patients  
632 who do not meet all the inclusion criteria at Visit 1 will be considered screen failures and will not  
633 be randomized to participate in the study.

634  
635 During this visit, the investigator will insert the CGM to obtain baseline information  
636 (before drug exposure). During this visit, patients will receive training on CGM use and reinforce  
637 SMBG diary collection. Trained personnel will proceed with sensor insertion. After that, the  
638 sensor will be activated, the CGM session will be started.

639  
640 Eligible patients will be trained on the use of the glucose meter to monitor their BG levels  
641 (i.e. 8-point SMBG). Patients will be given diabetes diaries and associated training to record all  
642 glucose levels, insulin doses, and episodes of hypoglycemia. Subcutaneous injections  
643 administration technique will be reviewed prior to randomization to ensure good technique.  
644 Reinforcement will be provided as needed during the follow-up visits.

645  
646 Patients will be instructed in performing glucose testing at home before meals, with a  
647 minimum of 2 out of the 4 pre-meal and/or bedtime glucose measurements per day. In addition,  
648 patients must perform an 8-point SMBG for at least 1 day prior to week 0, 12, 26, as follows:

649  
650  
651 **Time-points for 8-point SMBG profile:**  
652

653 The blood glucose levels should be measured and recorded in the diary (including date,  
654 actual clock time and blood glucose value) at the following time points, always starting with

655 measurement before breakfast. Subjects will be instructed to collect the SMBG on a day where  
656 the subject does not anticipate unusual strenuous exercise.

657 • Before breakfast  
658 • 90 min after the start of breakfast  
659 • Before lunch  
660 • 90 min after the start of lunch  
661 • Before dinner  
662 • 90 min after the start of dinner  
663 • At bedtime  
664 • In the middle of the night at 3 or 4 am

665 Subject will also be instructed to check and record BG when hypoglycemia is suspected. Values  
666 < 70 mg/dl should trigger an intervention, as described below (safety section).

667

668 Instructions for Run-In Period (2 weeks):

669 The main purpose of this period is to ensure that patients can comply with 8-point SMBG, pen  
670 instructions and trial recommendations.

- 671 • Oral antidiabetic agents will be continued at same dose until randomization visit.  
672 Metformin dose will be titrated up to 1000mg twice daily or to the maximum tolerated  
673 dose, unless contraindicated, per investigator's discretion.
- 674 • Basal Insulin therapy [NPH, mixed insulin, or basal insulin (glargine U100, detemir)] at  
675 TDD ≤50 units will continue at same insulin dosage until randomization. Insulin can be  
676 initiated, or dose could be increased during run-in period in those subjects with severe  
677 hyperglycemia (BG>300 mg/dL) and/or glucotoxicity per investigator's discretion, for  
678 subject's safety reasons.
- 679 • Patients will be instructed in performing glucose testing at home before meals, with a  
680 minimum of 2 out of the 4 pre-meal and/or bedtime glucose measurements per day.
- 681 • Patient not randomized in the trial will be considered screening failures, and no data will  
682 be collected since these patients will not receive study medication.

683

684

685

686 Preparation for Visit 2 (Randomization visit)

- 687 • Patient will be instructed to complete the 8-point SMBG, and to titrate up metformin,  
688 unless contraindicated.
- 689 • All patients will be instructed to provide daily glucose records. In addition, they will

690                   perform an 8-point SMBG done prior to Visit 3 (as described above).

691     • Patients who complied with the 8-point glucose testing (up to 6 points) and fulfill the

692                   eligibility criteria at Visit 2 will be randomized to participate in the study.

693     • Reminder to bring CGM sensor for collect and download.

694

695

696     **Randomization (Visit 2, Week 0)**

697     • Patients will be randomized to each treatment group

698     • Continue metformin therapy at same dose, unless contraindicated or for safety issues

699     • Discontinue other OADs and insulin formulation

700     • If BG > 400 mg/dl, patients will not be randomized, and considered screening failures.

701     • If BG > 300 mg/dl, investigator may order a confirmatory glucose test (at a different time)

702                   before considering the subject screen failure.

703     • Subjects will receive detailed instruction on the use of the IDegLira pen or IDeg and

704                   Aspart Pens and the titration algorithm.

705     • Patient will receive study medications. Subjects randomized to IDegLira will be

706                   instructed to not exceed 50 dose steps and to notify investigators if needed.

707     • Dose of insulin will be adjusted as needed.

708

709     • Patients will be instructed in performing glucose testing at home before meals, with a

710                   minimum of 2 out of the 4 pre-meal and bedtime glucose measurements per day.

711     • Patients will complete the DTSQ and TRIM-D questionnaires

712     • Investigator will collect CGM sensors

713

714

715     **Telephone Visits (weeks 1, 2, 3, 5, 6, 7, 10, 16, and 24)**

716     • Between each office visit, subjects will have a telephone visit with study personnel

717     • The purpose of these visits will be to monitor compliance with SMBG, CGM use, and

718                   study medication. Also hypoglycaemia and hyperglycemia data, as well as AEs, will be

719                   collected.

720     • Study diaries will be collected and reviewed for BG levels, episodes of hypoglycemia,

721                   SQ injections self-administration.

722

723     **Follow-up Visits (visit 6-18)**

724     The following activities will occur during interim visits:

725     • Subjects will receive detailed instruction on the use of the insulin or IDegLira pens

726     • Study diaries will be collected and reviewed for BG levels, episodes of hypoglycemia,

727                   insulin self-administration

728           • Dose of IDeglira or insulin will be adjusted as needed. Study medication will be  
729            dispensed

730           • Subjects will be instructed in performing glucose testing at home before meals, with a  
731            minimum of 2 out of the 4 pre-meal and bedtime glucose measurements per day.

732           • Drug compliance will be reviewed (see below "subject compliance" section)

733           • AE and hypoglycemia data will be collected, as well as concomitant medications.

734           • Laboratory blood work as indicated on page 12 (schedule of events during study  
735            period)

736

737

738           **Visit 12 (12 weeks follow up)**

739           The following activities will occur during interim visits:

740           • Study diaries (8p-SMBG) will be collected and reviewed for BG levels, episodes of  
741            hypoglycemia, insulin self-administration

742           • Dose compliance will be reviewed

743           • Dose of IDeglira or insulin will be adjusted as needed. Dispensing study medication.

744

745           • Body measurements, vital signs, BMI will be collected

746           • HbA1c, Fasting Glucose/CMP and pregnancy test (WOCP per PI discretion) will be  
747            obtained

748           • CGM will be inserted

749           • Patients will complete the DTSQ and TRIM-D questionnaires

750           • AE and hypoglycemia data will be collected, as well as concomitant medications.

751           • Drug dispensing

752

753           **CGM visits (insertion on weeks -2, 12, 26 and collection on week 0, 14, 27)**

755           All enrolled participants will have a blinded/professional CGM study performed during  
756           week -2, 12, and 26 weeks of follow-up.

757           During this visit, participants will receive training on CGM use and reinforce SMBG diary  
758           collection. Trained personnel will proceed with sensor insertion, transmitter placement and  
759           hook-up. After that, the transmitter will be activated, the CGM session will be started.

760           After 7 days, subjects will remove the sensor and return to the scheduled visit. Transmitter  
761           will be connected to the computer for data downloading. CGM summary will be reviewed to  
762           determine the quality.

763           Sensor will be stored following standard precautions. Onsite visits will be allowed for upload of  
764           the study devices and face-to-face discussion about hypoglycemia and hyperglycemia

765 episodes, insulin doses, AE/SAE evaluation, and replacement of study medication, if required.  
766 Trained personnel will input required clinical and demographic data into the sensor database  
767 software. Subjects will complete an 8-point SMBG for 1 day (as shown in Table 1) prior to clinic  
768 visit. Subjects will bring their glucose meter, CGM sensor (if applicable), BG diary, to each  
769 onsite visit.

770 **Visit 17 (Week 26, end-of-study)**

- 771 • Diabetes Treatment Satisfaction Questionnaire Status (DTSQs) and TRIM-D survey
- 772 • Blood sampling as indicated on page 12- schedule of events during the study period,  
773 including HbA1c assessment to determine efficacy of treatment
- 774 • Study diaries collected and reviewed for BG levels, episodes of hypoglycemia, insulin  
775 self-administration

776

777 **Visit 18 (week 27, case sign-off)**

- 778 • This visit should occur at least one week after the last treatment visit
- 779 • Since degludec has a prolonged duration of action, this visit will serve to monitor for  
780 adverse events.
- 781 • Sensor removal (after 7 days).

782 During each visit, participants will have their insulin dose titrated to achieve a fasting  
783 glucose 70-100 mg/dL as detailed in the insulin titration algorithm. Once the fasting glucose 3-  
784 day average is <100 mg/dL, insulin doses will be kept constant, unless the participant  
785 experiences recurrent or severe hyperglycemia.

786  
787  
788  
789  
790

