### 851 **Other Assessments**

852 We will assess patient satisfaction by using the DTSQs at baseline and the DTSQc at the end-  
853 of-study, as recommended by Health Psychology Research.

854 For treatment satisfaction, subjects' responses to questions 1, 7 and 8 of the DTSQc will be  
855 used. A comparison of the score on the DTSQs from week 0 to week 24, as well as using the  
856 score on the other questions of the DTSQc, which would overcome the ceiling limitation of using  
857 the DTSQs by itself. The Diabetes Treatment Satisfaction Questionnaire Status (DTSQs) form  
858 will be administered at weeks 0, 12 and the DTSQc will be administered at week 26. The  
859 amplitude of the score on the DTSQc gives the degree of change in satisfaction, while the  
860 direction (positive or negative) will provide guidance on the preference of one treatment regimen  
861 over the other one.

862 For quality of life, we will use the "Treatment-related impact measures for diabetes" (TRIM-D)"  
863 in order to determine the impact of the type of therapy on this outcome. Subjects will be given  
864 the questionnaire at baseline, and weeks 12 and 26 to assess their quality of life and any  
865 potential impact of the treatment regimen .

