### 997 **Randomization and Blinding**

998 This is an open label randomized controlled trial. Patients will be randomized  
999 consecutively using a computer-generated randomization table provided by [name],  
1000 Professor of Statistics at the Emory School of Public Health. Patient will be randomized based  
1001 on HbA1c (HbA1c <10 or ≥10). The randomization table will be mailed to each institution where

1002 a member of the research team will be in charge of the randomization process and group  
1003 assignment.

1004 **Breaking of Blinded Codes**

1005 N/A

1006

1007

1008 **CONCOMITANT ILLNESSES AND MEDICATIONS:**

1009 **Definitions:**

1010 Concomitant illness: any illness that is present at the start of the trial (*i.e. at the first visit*).

1011 Concomitant medication: any medication other than the trial product(s) that is taken during the  
1012 trial, including the screening and run-in periods.

1013 Details of all concomitant illnesses and medication must be recorded at trial entry (*i.e. at the first*  
1014 *visit*). Any changes in concomitant medication must be recorded at each visit. If the change  
1015 influences the subject's eligibility to continue in the trial, the sponsor must be informed.

1016 The information collected for each concomitant medication includes, at a minimum, start date,  
1017 stop date or continuing, and indication.

1018 For each concomitant illness, date of onset, date of resolution or continuing, at a minimum,  
1019 should be recorded.

1020

1021 **ADVERSE EVENTS:**

1022 The investigator will be responsible for reporting of all adverse events including serious  
1023 adverse events (SAE), serious adverse drug reactions (SADRs) to the competent authority and  
1024 independent IRB boards based upon federal regulations and local/IRB policies. The investigator  
1025 will report to the sponsor all S A R D s at the same time it's reported to the IRB or within 15  
1026 days of the investigator becoming aware.

1027 The investigators will collect the following information at minimum for each of these events:

1028 1. Study name

1030 2. Patient identification (e.g. initials, sex, age)

1031 3. Diagnosis

1032 4. Drug

1033 5. Reporter identification (e.g. Name, or initials)

1034 1035 Also 6) Causality, and 7) Outcome might be reported, but this is not mandatory.

1036

1037

1038

1039

1040 **Definitions**

1041 **Adverse Event (AE):**

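### The Visit 2 list puts the baseline DTSQs and TRIM-D after open-label allocation, training and dispensing, and nothing requires them to be completed before the arm is disclosed

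*Combined protocol and SAP*

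**What the plan says.** Randomization and Blinding states: "This is an open label randomized controlled trial". Patients therefore know their arm once it is assigned.

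The section Randomization (Visit 2, Week 0) is an unnumbered list of eleven bullets. The first reads "Patients will be randomized to each treatment group". Later ones stop other agents, give pen training ("Subjects will receive detailed instruction on the use of the IDegLira pen or IDeg and" aspart pens) and dispense ("Patient will receive study medications"). The tenth is "Patients will complete the DTSQ and TRIM-D questionnaires".

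Table 1 marks the DTSQ and TRIM-D at V2, V12 and V17. V2 is also the randomization visit, and the table sets no order within it.

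Other Assessments treats this administration as the baseline. The DTSQs is given at weeks 0 and 12, and a DTSQs change from week 0 is planned. The DTSQc follows at week 26. For TRIM-D, patients receive "the questionnaire at baseline, and weeks 12 and 26 to assess their quality of life and any" effect of the regimen.

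Statistical Methods plans cross-sectional comparisons first for outcomes measured repeatedly, then repeated-measures ANOVA and regression. It does not say whether week 0 enters as a response or as a covariate.

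**The concern.** Aim 3 hypothesizes higher satisfaction and adherence with IDegLira. The arms differ in what these forms are meant to capture: the background section sets one daily injection against as many as five. A patient who has just learned the arm, been trained on its pens and been handed the drug may rate satisfaction or treatment burden differently from one who has not.

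A score taken at that moment is a post-randomization measurement carrying a baseline label. If the reaction differs by arm, randomization no longer balances the week-0 score in expectation, and an analysis that subtracts it or adjusts for it carries the imbalance into the treatment contrast. A larger sample would not remove this, and it could not be reliably repaired after data collection.

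**Working it through.** The documents state no figure for Aim 3 (no sample size, SD or expected difference), so there is nothing of the plan's own to reproduce. The check is a comparison of sections, followed by simple algebra.

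**Is the order fixed anywhere?**

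- Visit 2 list: forms tenth, randomization first, training sixth, dispensing seventh.
- Table 1: same visit, no order.
- Other Assessments: week 0 or baseline, no order.
- Screening visit text: the baseline CGM is expressly placed ahead of drug exposure, and injection technique is reviewed ahead of randomization. The plan therefore fixes timing for some items, but the questionnaires have no equivalent instruction.

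**Is the list a sequence?** Not strictly. The fourth bullet says "If BG > 400 mg/dl, patients will not be randomized, and considered screening failures", yet it stands after the randomization bullet. The Visit 12 list also mentions dispensing both before the measurements and again at the end. The order on the page therefore does not prove the order in the clinic.

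**Which analyses use week 0?**

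- Use it: DTSQs change, TRIM-D change, and any repeated-measures or baseline-adjusted contrast that includes week 0.
- Do not use it: the week-26 DTSQc, which asks about change directly; between-arm comparisons of week-12 or week-26 scores alone; and HbA1c, whose baseline sample is taken at V1, before randomization.

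**What would a late baseline do?** Let disclosure move the mean week-0 score by d more in the IDegLira arm than in the basal-bolus arm. Follow-up scores are taken to be the same under either order, since patients know their arm by then.

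- Change from baseline: estimated difference = true difference − d.
- Baseline-adjusted with slope b: estimated difference = true difference − b × d.

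Neither d nor b is in the documents. For assumed d of 0.1, 0.2 and 0.3 SD and assumed b of 0.3 to 0.7:

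- d = 0.1: change-score bias 0.1 SD; adjusted bias 0.03 to 0.07 SD.
- d = 0.2: change-score bias 0.2 SD; adjusted bias 0.06 to 0.14 SD.
- d = 0.3: change-score bias 0.3 SD; adjusted bias 0.09 to 0.21 SD.

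**Scale.** The plan recruits 75 per arm and allows 20% attrition: 75 × 0.8 = 60. For an outcome with SD 1, the standard error of a between-arm difference is √(2/60) = 0.18. The change score also has SD 1 if the two time points have equal SDs and correlation 0.5 (assumed), because 2 × (1 − 0.5) = 1. On that footing a shift of 0.2 SD is about one standard error.

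**The case against.** The strongest reply is that the bullets are a checklist. The glucose bar to randomization is listed after randomization, so a site reading the list literally would randomize before checking whether it may. The documents call the week-0 forms a baseline, and an experienced coordinator would probably give them first. This stands in part: a reader might infer that the protocol schedules a post-allocation baseline, and the documents do not support that. They leave the order open. But the glucose bullet shows by its own wording that it comes before randomization, whereas the questionnaire bullet carries no such cue.

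A second reply is that Aim 3 does not rest on week 0 alone. That is right for the DTSQc and for comparisons at week 12 or 26, so it would be wrong to infer that Aim 3 as a whole is compromised. It does not protect the DTSQs change or the TRIM-D change.

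A third is that patients know their arm at weeks 12 and 26 anyway, so reordering Visit 2 leaves open-label influence on follow-up scores untouched. This is true. The fix protects only the baseline.

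A reader might also infer that the bias favors IDegLira. The documents do not show that. Pleasure at drawing the simpler regimen would raise the IDegLira baseline and hide a benefit; marking the old regimen down against the new one would exaggerate it.

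**Conclusion.** The point holds as a missing safeguard. The plan permits, and its list suggests, completing the baseline DTSQs and TRIM-D after the open-label arm is known. Bias then requires two things that the documents do not establish: that sites do complete the forms late, and that disclosure moves the arms apart. Given both, the error is d in a change-score contrast and b × d in a baseline-adjusted one, with size and direction unknown; the SD figures above are illustrations only. The exposure is confined to secondary patient-reported contrasts that use week 0. The non-inferiority conclusion on HbA1c and the sample size are not touched. It is worth correcting because the remedy costs almost nothing.

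**What to change.** In the Visit 2 list, move the questionnaire bullet to the top and state that the DTSQs and TRIM-D are completed and collected at Visit 2 before the randomization table is consulted and the arm disclosed. Repeat this in a Table 1 footnote. At most, add a box on the form recording whether it was completed before allocation.

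Moving the forms into the run-in is not a good alternative. It conflicts with the week-0 timing, and treatment may change in that period: metformin is titrated, and insulin may be started or increased. Nor is a rule needed that discards late forms.

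The cost is one sentence and one footnote, with the same forms, visit, staff and sample size.
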